## 7.8 General Concomitant Medication and Supportive Care Guidelines

Metformin and pembrolizumab are not affected by p450 enzymes and therefore p450 inhibitors are allowed.

Concomitant use of furosemide results in increased levels of metformin and therefore should be avoided if possible but is allowable if needed for diuresis with close monitoring.

Cationic drugs (e.g., amiloride, digoxin, morphine, procainamide, quinidine, quinine, ranitidine, triamterene, trimethoprim, or vancomycin) that are eliminated by renal tubular secretion

theoretically have the potential for interaction with metformin by competing for common renal tubular transport systems. Therefore, these medications are to be avoided if possible while patient is on study but are allowable if felt to be necessary by patient's physician. However, it must be documented that patient was on these medications.

Nifedipine results in enhanced absorption of metformin. It must be documented if a patient is on nifedipine during the study but is allowable.

Subjects are prohibited from receiving the following therapies during the Screening and Treatment Phase of this trial:

- Biological therapy
- Immunotherapy not specified in this protocol
- Chemotherapy
- Investigational agents other than pembrolizumab or metformin
- Live vaccines within 30 days prior to the first dose of trial treatment and while participating in the trial. Examples of live vaccines include, but are not limited to, the following: measles, mumps, rubella, varicella/zoster, yellow fever, rabies, BCG, and typhoid vaccine.
- Systemic glucocorticoids should be avoided if possible. Steroids are allowed as short bursts of 5-7 days if required for clinical indication (i.e. COPD) or to modulate symptoms from an adverse event of suspected immunologic etiology. The chronic use of physiologic doses of corticosteroids may be approved after consultation with the Sponsor Investigator.

Subjects, who, in the assessment by the investigator, require the use of any of the aforementioned treatments for clinical management other than specified as allowed, should be removed from the trial. Subjects may receive other medications that the investigator deems to be medically necessary.

There are no prohibited therapies during the Post-Treatment Follow-up Phase.

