## 7.4 Agent Administration

Treatment will be administered on an outpatient basis. Reported adverse events and potential risks are described in the Investigators Brochure for Pembrolizumab and the package insert for Metformin. Appropriate dose modifications are described in Section 8. No investigational or commercial agents or therapies other than those described below may be administered with the intent to treat the patient's malignancy.

Regimen Description					
Agent	Premedications; Precautions	Dose	Route	Schedule	Cycle Length
Pembrolizumab	No premedications; No steroids	200mg or 400mg	IV over 30 minutes	Days 1, week 1 (for 400mg	21 days (3 weeks)

				dose, therapy only given q6 weeks and on odd cycles)	
Metformin*	No premedications	1000mg for first 7 days followed by 2000mg daily	Oral	Daily	Continuous**

* The patient will be requested to maintain a medication diary of each dose of medication. The medication diary will be returned to research staff at the end of each course.
 
** Metformin will be escalated per schema and then given continuously throughout pembrolizumab cycles.
					

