### 7.7.2 Dose Limiting Toxicity

Dose limiting toxicity (DLT) is defined as the appearance of side effects during treatment that are attributed to treatment and severe enough to prevent continuation of treatment or grade 3 or 4 non-hematologic toxicities other than alopecia, nausea or vomiting and that in the case of pembrolizumab, do not resolve with steroids after four weeks. If more than three of nine patients develop a DLT, then combination will be considered unsafe and the study will not proceed. Patients are assessed for DLTs during the lead-in period as well as for the first 28 days of combination treatment.

Management and dose modifications associated with the above adverse events are outlined in Section 8.

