#### 8.2.4 Dose Discontinuation of Pembrolizumab

Treatment should be permanently discontinued for the following:

- Any Grade 2 drug-related uveitis or eye pain or blurred vision that does not respond to topical therapy and does not improve to Grade 1 severity within the re-treatment period OR requires systemic treatment.
- Any Grade 3 non-skin, drug-related adverse event lasting > 7 days, with the following exceptions for drug-related laboratory abnormalities, uveitis, pneumonitis, bronchospasm, neurologic toxicity, hypersensitivity reactions, and infusion reactions:
  - Grade 3 drug-related uveitis, pneumonitis, bronchospasm, neurologic toxicity, hypersensitivity reaction, or infusion reaction of any duration requires discontinuation.
  - Grade 3 drug-related laboratory abnormalities do not require treatment discontinuation except:
    - Grade 3 drug-related thrombocytopenia > 7 days or associated with bleeding requires discontinuation
    - Any drug-related liver function test (LFT) abnormality that meets the following criteria require discontinuation:
      - AST or ALT > 8 x ULN
      - Total bilirubin > 5 x ULN
      - Concurrent AST or ALT > 3 x ULN and total bilirubin > 2 x ULN
- Any Grade 4 drug-related adverse event or laboratory abnormality, except for the following events which do not require discontinuation:
  - Isolated Grade 4 amylase or lipase abnormalities that are not associated with symptoms or clinical manifestations of pancreatitis and decrease to < Grade 4 within 1 week of onset.
  - Isolated Grade 4 electrolyte imbalances/abnormalities that are not associated with clinical sequelae and are corrected with supplementation/appropriate management within 72 hours of their onset.
- Any dosing delay lasting > 8 weeks with the following exceptions:
  - Dosing delays to allow for prolonged steroid tapers to manage drug-related adverse events are allowed. Prior to re-initiating treatment in a subject with a dosing delay lasting > 8 weeks, the PI must be consulted. Tumor assessments should continue as per protocol even if dosing is delayed.
  - Dosing delays > 8 weeks that occur for non-drug-related reasons may be allowed if approved by the PI. Prior to re-initiating treatment in a subject with a dosing delay lasting > 8 weeks, the PI must be consulted. Tumor assessments should continue as per protocol even if dosing is delayed.

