Stop the pembrolizumab infusion, begin an IV infusion of normal saline, and treat the subject with diphenhydramine 25-50 mg IV (or equivalent) and/or acetaminophen 325 to 1000 mg; remain at bedside and monitor subject until resolution of symptoms. Corticosteroid or bronchodilator therapy may also be administered as appropriate. If the infusion is interrupted, then restart the infusion at 50% of the original infusion rate when symptoms resolve; if no further complications ensue after 30 minutes, the rate may be increased to 100% of the original infusion rate. Monitor subject closely. If symptoms recur then no further pembrolizumab will be administered at that visit. Administer diphenhydramine 25-50 mg IV, and remain at bedside and monitor the subject until resolution of symptoms. The amount of study drug infused must be recorded on the electronic case report form (eCRF). The following prophylactic premedications are recommended for future infusions: diphenhydramine 25-50 mg (or equivalent) and/or acetaminophen 325 to 1000 mg should be administered at least 30 minutes before additional pembrolizumab administrations. If necessary, corticosteroids (recommended dose: up to 25 mg of IV hydrocortisone or equivalent) may be used.

**For Grade 3 or Grade 4 symptoms:** (Severe reaction, Grade 3: prolonged [i.e., not rapidly responsive to symptomatic medication and/or brief interruption of infusion]; recurrence of symptoms following initial improvement; hospitalization indicated for other clinical sequelae)

[e.g., renal impairment, pulmonary infiltrates]). Grade 4: (life threatening; presser or ventilator support indicated).

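### Section 7.8 removes from the trial a patient who needs more than a short steroid burst for an immune-related event, while 8.2.4 allows a prolonged taper with re-treatment

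*Combined protocol and SAP*

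**What the plan says.** All references are to the combined protocol and SAP.

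- **7.8 (concomitant medication).** Systemic glucocorticoids appear in the list of therapies prohibited during screening and treatment. The entry permits: "Steroids are allowed as short bursts of 5-7 days if required for clinical indication (i.e. COPD) or to modulate symptoms from an adverse event" (thought to be immune-related). It adds: "The chronic use of physiologic doses of corticosteroids may be approved after consultation with the Sponsor Investigator". The closing rule is that subjects who "require the use of any of the aforementioned treatments for clinical management other than specified as allowed, should be removed from the trial".
- **8.2.4 (pembrolizumab discontinuation).** Delays beyond 8 weeks lead to permanent discontinuation, with exceptions. One is: "Dosing delays to allow for prolonged steroid tapers to manage drug-related adverse events are allowed". The PI must be consulted before re-treatment, and tumor assessments carry on during the delay.
- **8.2.3 (criteria to resume).** A delay beyond 8 weeks means permanent discontinuation of study therapy. No taper exception is stated.
- **7.7.2 (DLT definition).** One limb covers attributed side effects severe enough to prevent continuing treatment. The other covers most Grade 3 or 4 non-hematologic toxicities which, for pembrolizumab, "do not resolve with steroids after four weeks".
- **7.4 (regimen table).** The premedication and precaution entry for pembrolizumab is "No premedications; No steroids".
- **8.2.5 (infusion reactions).** Premedication is recommended for later infusions after Grade 1 or 2 reactions. After Grade 2: "If necessary, corticosteroids (recommended dose: up to 25 mg of IV hydrocortisone or equivalent) may be used".

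**The concern.** Immune-related events are a foreseeable result of pembrolizumab, and the protocol's background says they are managed mostly with steroids. For a patient who needs more than a short burst, above physiologic dose, 7.8 and 8.2.4 prescribe different fates: removal from the trial, or a taper under continued observation with possible re-treatment. Section 8.2.1 sends sites to the investigator's brochure and to institutional guidelines, so it does not settle the matter.

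Three things depend on the answer:

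- **Response.** Section 13.1.1 counts a patient as evaluable only with measurable disease, at least one cycle of therapy and a re-evaluation (or early objective progression). Removal before the first re-evaluation can take the patient out of the planned 19.
- **DLT count.** An event that forces removal may be counted under the first limb of 7.7.2. The same event managed with a taper and resolving in time need not count. The stopping decision turns on three of nine patients (10.3) or more than three of nine (7.7), so one classification can decide it.
- **Follow-up.** Section 7.5.8 separates withdrawal from treatment from withdrawal from study, and 7.10 follows patients removed from treatment. Section 7.8 speaks of removal from the trial, which leaves PFS and OS follow-up unclear.

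**Working it through.** The plan has no figure of its own on this point, so the check is a comparison of the sections followed by a sense of scale.

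**Step 1. One patient, two sections.** Take a patient with an immune-related event who needs steroids for more than 7 days, above physiologic dose.

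| Section | Consequence |
|---|---|
| 7.8 | Beyond the 5-7 day burst and outside the physiologic-dose exception, so removed from the trial |
| 8.2.4 | Prolonged taper allowed; delay may pass 8 weeks; re-treatment after PI consultation; scans continue |
| 8.2.3 | If the delay passes 8 weeks, study therapy stops permanently |
| 7.7.2 | Resolution on steroids judged at four weeks |

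Removal from the trial cannot be combined with continued scans and re-treatment. Sections 8.2.3 and 8.2.4 also differ from each other once the delay passes 8 weeks.

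**Step 2. Durations.** Four weeks is 28 days: 28/7 = 4 and 28/5 = 5.6, so the resolution window in 7.7.2 is 4 to 5.6 times the burst length in 7.8. Eight weeks is 8 x 7 = 56 days. A taper long enough to need the exception in 8.2.4 would be far outside a 5-7 day allowance.

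**Step 3. How many patients.** The documents give no rate of immune-related events needing steroids for more than 7 days. The only related figure is 6.3% Grade 3 or higher immune-related events on pembrolizumab in the first-line study cited in 3.2.1. As a rough illustration:

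- Expected in 25 enrolled: 25 x 0.063 = 1.6.
- At least one in 25: 1 - (1 - 0.063)^25 = 0.80.
- At least one in the nine lead-in patients: 1 - (1 - 0.063)^9 = 0.44.

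These are not counts of patients caught by the conflict. Section 8.2.4 already stops pembrolizumab for many Grade 3 events lasting more than 7 days, for several Grade 3 types of any duration and for nearly all Grade 4 events. Conversely, lower-grade events needing longer steroids are not in the 6.3%. The 0.44 also makes no allowance for the length of the DLT window.

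**Step 4. Effect of one patient on the response rate.** Start from the success criterion in 10.2, 6/19 = 31.6%.

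- Non-responder drops out of the evaluable set: 6/18 = 33.3%, a change of +1.8 points.
- Responder drops out: 5/18 = 27.8%, a change of -3.8 points.
- Responder stays in the denominator but is counted as a non-responder: 5/19 = 26.3%, a change of -5.3 points. This is the upper bound.

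**The case against.** The best defense is that the sections can be read together. The removal clause in 7.8 exempts what is specified as allowed without limiting that to 7.8, and 8.2.4 allows prolonged tapers. The sentence in 7.8 could also be parsed so that the 5-7 day limit attaches only to indications such as COPD. Section 7.7.2 points to Section 8 for managing these events, and 8.2 is specific where 7.8 is general. These readings are possible, but none is stated. The pointer to Section 8 does not switch off the removal clause, and the natural reading of the sentence puts immune-related events under the burst limit.

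Other parts of the defense do stand, and they rule out stronger readings that a reader might infer:

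- *Sites already act differently.* The documents do not say so. Section 7.3.5 requires consultation with the coordinating PI for interruptions over 4 weeks, and all active sites review lead-in DLTs monthly (7.7.1). Divergent handling is a possibility only.
- *The DLT definition permits a four-week steroid course.* It sets a point for judging resolution; it neither permits nor requires continuous steroids.
- *Removal makes a DLT impossible to observe.* The first limb of 7.7.2 could still be met, and adverse events are followed after treatment stops (7.5.8, 7.10, 11.4).
- *The regimen table flatly contradicts 8.2.5.* Its entry can be read as the default for routine infusions, with 8.2.5 as the exception after a reaction. This is a smaller matter of wording.
- *Every removed patient is lost to the primary endpoint.* A patient who has received at least one cycle and is removed after the first re-evaluation remains evaluable (13.1.1).

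**Conclusion.** The conflict between 7.8 and 8.2.4 is real and should be corrected. Followed literally, 7.8 takes out of the trial patients whom 8.2.4 keeps under treatment and assessment, and nothing says which governs. Section 8.2.3 adds a second mismatch by stating the 8-week limit without the taper exception.

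The conclusion rests on the natural reading of 7.8 and applies only to patients needing more than a short burst outside the physiologic-dose exception. How many there will be cannot be derived from the documents. The illustration of 1.6 in 25 assumes that the cited rate carries over and that each such event needs more than 7 days of steroids, and it includes many whose pembrolizumab stops anyway. Per patient, the shift at 6/19 is +1.8 or -3.8 points. A reader might quote 5.3 points per patient, but that holds only if a responder is retained and recorded as a non-responder. In the lead-in, one event classified differently could matter at the stopping boundary.

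**What to change.** Reconcile 7.8 with 7.7.2, 8.2.3 and 8.2.4, and 7.4 with 8.2.5, so that one steroid rule is written once and cited by the others. It should:

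1. Treat separately immune-related events, other indications, and premedication after an infusion reaction.
2. State whether exceeding a limit stops one drug, all study treatment or trial participation.
3. State that response assessment and survival follow-up continue unless consent is withdrawn.
4. Say how an event in the lead-in is classified under 7.7.2 when the steroid rule, rather than the toxicity alone, ends treatment.

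The clinical limit itself is for the sponsor's clinicians to choose. The cost is wording in the next amendment, with no new procedures. If any patient has already received steroids beyond a burst, record which rule was applied and keep that patient's response and DLT status traceable.

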## 7.9 Duration of Therapy

In the absence of treatment delays due to adverse event(s), treatment may continue until one of the following criteria applies:

- Disease progression
- Intercurrent illness that prevents further administration of treatment
- Unacceptable adverse event(s)
- Patient decides to withdraw from the study
- General or specific changes in the patient's condition render the patient unacceptable for further treatment in the judgment of the investigator

- Clinical progression
- Patient non-compliance
- Pregnancy
  - All women of child bearing potential should be instructed to contact the investigator immediately if they suspect they might be pregnant (*e.g.*, missed or late menstrual period) at any time during study participation.
  - The investigator must immediately notify the sponsor in the event of a confirmed pregnancy in a patient participating in the study.
- Termination of the study by the UC PI (coordinating center PI).
- The drug manufacturer can no longer provide the study agent

The reason(s) for protocol therapy discontinuation, the reason(s) for study removal, and the corresponding dates must be documented in REDCap.

## 7.10 Duration of Follow-Up

Patients will be followed for survival up to five years after removal from treatment or until death, whichever occurs first. Patients removed from treatment for unacceptable adverse event(s) will be followed until resolution or stabilization of the adverse event but will also continue to be followed for survival up to five years.

## DOSING DELAYS/DOSE MODIFICATIONS

### 8.1 Metformin ER

Acceptable Dose Reductions for Metformin ER	
Dose Reduction Level	Dose Reduction
1	1000mg
2	500mg

Diarrhea	Management/Next Dose for Metformin ER
≤ Grade 2	No change in dose- can use loperamide to control
Grade 3**	Hold until ≤ Grade 2. Resume at same dose level. Decrease dose to 1000mg daily. Second occurrence can decrease to 500mg daily. Third occurrence, discontinue permanently.
Grade 4	Off protocol therapy
*Patients requiring a delay of >4 weeks should go off protocol therapy.	
**Ensure diarrhea is not due to pembrolizumab (see criteria below).	

Diarrhea	Management/Next Dose for Metformin ER

Recommended management: Loperamide antidiarrheal therapy  Loperamide dosage schedule: 4 mg at first onset, followed by 2 mg with each loose motion until diarrhea-free for 12 hours (maximum dosage: 16 mg/24 hours)  Adjunct anti-diarrheal therapy is permitted and should be recorded when used.
	

Nausea	Management/Next Dose for Metformin ER
≤ Grade 1	No change in dose
Grade 2	Hold until ≤ Grade 1. Resume at same dose level.
Grade 3	Hold* until < Grade 2. Resume at one dose level lower, if indicated.**
Grade 4	Off protocol therapy
*Patients requiring a delay of >4 weeks should go off protocol therapy.	
**Patients requiring > two dose reductions should go off protocol therapy.	
Recommended management: antiemetics.	

Vomiting	Management/Next Dose for Metformin ER
≤ Grade 1	No change in dose
Grade 2	Hold until ≤ Grade 1. Resume at same dose level.
Grade 3	Hold* until < Grade 2. Resume at one dose level lower, if indicated.**
Grade 4	Off protocol therapy
*Patients requiring a delay of >4 weeks should go off protocol therapy.	
**Patients requiring > two dose reductions should go off protocol therapy.	
Recommended management: antiemetics.	

Hypoglycemia	Management/Next Dose for Metformin ER
≤ Grade 1	No change in dose
Grade 2	Hold until ≤ Grade 1. Resume at same dose level.
Grade 3	Hold* until < Grade 2. Resume at one dose level lower, if indicated.**
Grade 4	Off protocol therapy
*Patients requiring a delay of >4 weeks should go off protocol therapy.	
**Patients requiring > two dose reductions should go off protocol therapy.	
Recommended management: antiemetics.	

**Lactic acidosis:** In a very small proportion of patients, lactic acidosis defined as lactate levels >5 can occur with metformin especially those with renal impairment. Due to the seriousness of this event, metformin should be permanently discontinued.

**Renal dysfunction:** Although metformin does not cause renal dysfunction, the clearance of metformin and therefore risk of lactic acidosis increases in renal dysfunction. Therefore, metformin dose should be decreased by 50% if eGFR is 30 to 45ml/min and held if eGFR is <30ml/min. Metformin may be restarted at full dose (using dose escalation as provided) once kidney function improves above these parameters.

**Vitamin B12 deficiency:** Metformin does not need to be held for this indication as long as B12 is replaced.

**Other Toxicities:** For any other grade 3-4 adverse events (besides those mentioned above), hold metformin until toxicities have recovered to grade 1 or less.

**Dose Reduction for Intolerability:** If patients have side effects that are considered intolerable to patient but are less than grade 3, support patients with supportive medications (loperamide, omeprazole, anti-emetics, etc.) and try alteration of their dosing schedule by reducing by 1 dose level at a time until toxicity is  $\leq$  grade 1 for 1 week. Then attempt to re-escalate to protocol dose. Every attempt should be made to keep metformin dose at protocol dose but if unable to achieve the assigned dose, then metformin should be maintained at highest dose tolerated for remainder of treatment.

NOTE: Temporarily discontinue metformin in patients undergoing radiologic studies in which intravascular iodinated contrast media are utilized. It is generally recommended that metformin be temporarily discontinued prior to or at the time of intravascular administration of iodinated contrast media (potential for acute alteration in renal function). Continue to withhold metformin for 48 hours after the radiologic study.

NOTE: If metformin is held at any time for any reason for longer than 1 week, upon restarting the drug, it must be dose escalated again slowly with 1000mg daily for 1 week prior to escalation to 2000mg daily.

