### 3.2.2 Metformin

Activation of the PI3K, Akt and the mammalian target of rapamycin complex 1 (mTORC1) signaling pathway was identified as being a prevalent molecular signature in many HNSCCs, resulting in potential strategies to target this pathway. In fact, activating mutations of the mTOR pathway are now recognized as drivers of some HNSCCs. However, targeting the mTOR pathway with rapamycin analogues, such as everolimus, results in undesirable side effects including mucositis, thrombocytopenia, and increased infection risk making combinatorial treatment with

systemic agents such as chemotherapy and radiation difficult. Interestingly, metformin has been shown to inhibit the mTOR pathway. Metformin is a biguanide and an oral antihyperglycemic agent, which is currently FDA approved for the treatment of type II diabetes. Specifically, metformin inhibits mTORC1 activity, through activation of the AMPK pathway resulting in decreased proliferation, metabolic synthesis and metastases in breast and colon cancer. Additionally, metformin inhibits HNSCC cell growth *in vitro* and prevents development and progression of oral cavity tumors in a HNSCC mouse tumor model supporting a role for metformin as a cancer preventative. The latter study demonstrated that metformin may also inhibit mTORC1 activity independent of AMPK activation. In line with these animal studies, retrospective population case-control cohort studies have demonstrated a decreased HNSCC risk in diabetic patients treated with metformin. In addition, metformin use resulted in a better overall survival in diabetic patients diagnosed with laryngeal squamous cell carcinoma. The potential impact of metformin use in non-diabetic HNSCC patients is unknown.

Metformin is widely used in many diabetic patients and overall well tolerated. Unlike other antihyperglycemic agents such as the sulfonylureas, metformin does not usually cause hypoglycemia. Adverse effects are relatively minimal with diarrhea being the most common cause of discontinuation. However, lactic acidosis, although rare (estimated incidence of 4.3 cases per 100,000 person-years in metformin users), is a serious adverse event resulting in up to 50% mortality when it occurs. Lactic acidosis has been associated with high plasma concentrations of metformin (>10mg/ml) which can occur in the presence of renal dysfunction. Therefore, careful

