#### 7.4.1 Metformin

##### *Treatment:*

Patients will receive metformin ER starting on day -14 for arm 1 and Day -7 for arm 2. The starting dose will be 1000mg PO daily to be administered with evening meal. The tablet should be swallowed whole, and patients will be instructed not to crush, cut or chew medication. On day -7 (or Day 1 for arm 2), patients will increase to 2000mg daily. Metformin will be continued daily with pembrolizumab.

Metformin should continue throughout treatment and even through pembrolizumab delays unless patient is experiencing adverse effects attributed to metformin. Metformin should be taken with food at approximately the same time daily. Patients will be instructed to check their blood sugar if they have any symptoms of hypoglycemia including but not limited to chills/shakiness, cold feeling, lightheadedness, dizziness, etc. Patients will be given a diary to record each dose. They should also be warned that the shell of the ER tablet may be visible in stool and not to be alarmed.

NOTE: Temporarily discontinue metformin in patients undergoing radiologic studies in which intravascular iodinated contrast media are utilized. It is generally recommended that metformin be temporarily discontinued prior to or at the time of intravascular administration of iodinated contrast media (potential for acute alteration in renal function). Continue to withhold metformin for 48 hours after the radiologic study.

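### Metformin dosing rules conflict: the dose after Grade 3 diarrhoea, the restart rule after a hold over 1 week, and the hold around iodinated contrast

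*Combined protocol and SAP*

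**What the plan says.** **Grade 3 diarrhoea (8.1).** Metformin is held until Grade 2 or lower, and then: "Resume at same dose level. Decrease dose to 1000mg daily. Second occurrence can decrease to 500mg daily. Third occurrence, discontinue permanently". A footnote limits the hold: "Patients requiring a delay of >4 weeks should go off protocol therapy".

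**Other Grade 3 toxicities (8.1).** The nausea, vomiting and hypoglycemia tables restart at one dose level lower, if indicated, with the same 4-week limit. In those tables an unchanged restart dose is the Grade 2 instruction, not the Grade 3 one.

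**Restart after a hold (8.1, closing note).** If metformin has been held for more than 1 week, at any time and for whatever reason, "it must be dose escalated again slowly with 1000mg daily for 1 week prior to escalation to 2000mg daily". No exception is stated.

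**Contrast (7.4.1 and 8.1).** Both sections carry the same note. It opens "Temporarily discontinue metformin in patients undergoing radiologic studies in which intravascular iodinated contrast media are utilized" and closes "Continue to withhold metformin for 48 hours after the radiologic study". The sentence between is phrased as a general recommendation. Footnote q of the Study Calendar leaves the same stop to the investigator's discretion.

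**The concern.** Dosing instructions for the investigational agent in a multi-site trial should give one answer. Here a site can follow the text and restart a patient at the dose that caused Grade 3 diarrhoea, or reduce the dose correctly and then be sent back to 2000 mg by the restart note.

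Section 3.2.2 says of metformin: "Adverse effects are relatively minimal with diarrhea being the most common cause of discontinuation". The dose-limiting toxicity definition in 7.7.2 exempts nausea and vomiting from its Grade 3-4 criterion, but not diarrhoea. Use of this cell is therefore plausible.

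The contrast hold exists because contrast can acutely alter renal function. Section 3.2.2 links renal dysfunction to lactic acidosis, which it calls rare but "resulting in up to 50% mortality when it occurs". As the text stands, two sites could handle the same contrast scan differently and both comply.

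**Working it through.** The plan gives no figure to reproduce on this point. The check traces the dose under each rule for a patient on the protocol dose of 2000 mg daily (section 7.4).

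**1. The diarrhoea cell alone.** The first sentence gives 2000 mg and the second gives 1000 mg. They cannot be read as successive episodes, because the second episode already has 500 mg and the third has permanent discontinuation. So 1000 mg can only be the first-episode dose. The two sentences agree only for a patient already on 1000 mg, for example in the run-in week.

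**2. The cell against the restart note.** Holds of more than 1 week and up to 4 weeks fall under both. The table gives 1000 mg, or optionally 500 mg after a second episode; the note gives 1000 mg for 7 days and then 2000 mg. The same clash arises whenever a Grade 3 nausea, vomiting or hypoglycemia reduction is taken. The intolerability paragraph of 8.1, which keeps patients at the highest dose they tolerate, does not settle it, because it covers only effects below Grade 3.

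**3. Size in milligrams.** Metformin over 28 days from restart:

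| Rule followed | Calculation | Total |
|---|---|---|
| Unchanged dose | 2000 × 28 | 56,000 mg |
| Reduced to 1000 mg | 1000 × 28 | 28,000 mg |
| Restart note | 1000 × 7 + 2000 × 21 | 49,000 mg |
| Reduced to 500 mg (second episode, if taken) | 500 × 28 | 14,000 mg |

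The restart note gives 49,000/28,000 = 1.75 times the reduced dose after a first episode, and 49,000/14,000 = 3.5 times after a second episode if the optional step to 500 mg is taken.

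**4. Contrast, side by side.** Sections 7.4.1 and 8.1 have an imperative to stop, a softer sentence on timing, and an imperative to withhold for 48 hours. Footnote q makes the stop discretionary. The mismatch is between sections. It can recur, because 7.6.3 prefers contrast CT at scheduled scans, although MRI is acceptable.

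**5. Cost of a firm contrast hold.** Section 7.4.1 starts metformin at "1000mg PO daily to be administered with evening meal". Assume evening dosing throughout and a daytime scan. A 48-hour hold then misses the scan-day and next-day doses, so 2 doses, or 3 if metformin is stopped the day before (assumed). Sections 7.6.3 and 13 give different scan intervals, 12 weeks (84 days) and 9 weeks (63 days), so both are shown:

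| Contrast scans in interval | 2 doses per scan | 3 doses per scan |
|---|---|---|
| One | 2/84 = 2.4% to 2/63 = 3.2% | 3/84 = 3.6% to 3/63 = 4.8% |
| Two (with the 4-week confirmation scan) | 4/84 = 4.8% to 4/63 = 6.3% | 6/84 = 7.1% to 6/63 = 9.5% |

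The cost is zero with MRI or non-contrast CT. Each hold is under 1 week, so the restart note is not triggered.

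**6. Background risk.** Section 3.2.2 quotes 4.3 lactic acidosis cases per 100,000 person-years. Over an assumed 25 patient-years, 25 × 4.3/100,000 = 0.0011 expected cases; over 10 to 50 patient-years, 0.0004 to 0.002. The documents give no rate for contrast given without a hold.

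**The case against.** **The diarrhoea cell resolves itself.** A careful reader can work out that 1000 mg is the first-episode dose. That is so, but a dosing table should not depend on the inference, and the unchanged-dose sentence comes first.

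**The specific rule governs the general one.** The restart note is plausibly meant only to prevent an abrupt return to full dose, and a toxicity table would ordinarily set the dose after that toxicity. As a reading of intent this stands. The wording, however, is mandatory, covers every reason for a hold and names 2000 mg as the end point.

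**Use of the cell is not shown.** This stands. The sentence in 3.2.2 calls adverse effects relatively minimal and concerns discontinuation, not Grade 3 events. The phase I discontinuations in the same section were at 2550 mg and 3000 mg daily, above this trial's dose, and the extended-release form was chosen to reduce side effects.

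**Footnote q may be deliberate.** This stands too. The notes contain softer wording, and the documents do not show which rule the sponsor intends. Renal safeguards also exist elsewhere: eligibility limits, serum chemistry every cycle, and dose reduction or hold by eGFR. A reader might infer that footnote q is simply an error and the strict hold the true rule. The documents support only that the two differ and one must govern.

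**Conclusion.** Minor, but wrong as written. The Grade 3 diarrhoea cell gives two incompatible restart doses at 2000 mg. The restart note, read literally, overrides the Grade 3 reductions in all four toxicity tables for holds of more than 1 and up to 4 weeks. The contrast instructions differ between 7.4.1 and 8.1 on one side and footnote q on the other.

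The 28-day totals illustrate the spread of doses for one patient. They do not measure impact on the trial, and the number of patients affected is not known.

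Two stronger inferences should be avoided. One is that the conflict biases the response rate or undermines the sample size or analyses; nothing in the documents shows this. The other is that about 0.001 expected lactic acidosis cases measures what a contrast hold would gain. It is a background expectation resting on assumed patient-years, and says nothing about risk after contrast.

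**What to change.** **Diarrhoea cell, 8.1.** Delete the first of the sentences quoted from the cell, which restarts at the unchanged dose. In place of the second, write: *First occurrence: resume at 1000 mg daily (or one dose level lower if already at or below 1000 mg).* Without the bracket, a patient already at 500 mg would have the dose raised. The reduction table lists nothing below 500 mg, so the sponsor should also say what happens to such a patient. Keep the second-occurrence step to 500 mg optional, as it is now, and keep permanent discontinuation at the third.

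**Restart note, 8.1.** Add: *Re-escalation to 2000 mg does not apply to patients whose dose was reduced for a Grade 3 toxicity under the tables above; they restart at the reduced dose.* The exception must cover all four tables. Limiting it to diarrhoea would imply that patients reduced for nausea, vomiting or hypoglycemia must return to 2000 mg.

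**Contrast.** The sponsor should choose one rule. The safer default is to align footnote q with 7.4.1 and 8.1. If discretion is intended, those two notes should be reworded instead.

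**Cost.** A clarification letter or short amendment. A firm contrast hold costs about 2 to 3 evening doses per contrast scan. Sample size, endpoints and analyses do not change.
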